7 STUDY TREATMENTS

7.1 Description of investigational medicinal products

Immediate-release BRV oral solution and immediate-release, film-coated BRV oral tablets will be provided during the study.

Brivaracetam oral solution at a concentration of 10mg/mL will be supplied in 300mL glass bottles.

Brivaracetam oral tablets will be provided in the following strengths; 10mg, 25mg, and 50mg.

There is no placebo or reference product.

7.2 Treatments to be administered

Brivaracetam (tablet and oral solution) should be administered bid approximately 12 hours apart in 2 equally divided doses. Subjects should be dosed with either oral tablets or oral solution and not a combination of both. The mg dosage for the oral tablet treatment should be calculated to match as closely as possible the mg/kg based dosage and should be a combination of the BRV 10mg, 25mg, and 50mg tablets. Only the following exact dosages are allowed for the oral tablet administration: BRV 20, 40, 50, 70, 100, 150, and 200mg/day.

The dose of oral solution will be measured using the appropriate syringes (1mL, 3mL, and/or 10mL) with an adaptor able to fit both bottle sizes. Oral solution should not be mixed with other liquids prior to administration.

Subjects should take their BRV treatment according to instructions provided by the Investigator. Dose adjustments for concomitant AEDs are allowed at any time based on clinical judgment.

Dispensation of IMP will be done by an interactive voice response system (IVRS).

7.2.1 Up-Titration Period for directly enrolled subjects

Beginning with Protocol Amendment 3, at TV1, eligible directly enrolled subjects will initiate treatment with BRV (oral solution or tablet, as appropriate).

The BRV dose will be titrated to optimize tolerability and seizure control. [Table 7-1](#) provides the recommended titration steps for the oral solution and tablet formulations. Subjects must be on the same daily dose for 7 ± 2 days before the dose is titrated to the next dosing level. Subjects may enter the Evaluation Period after they have remained on the same daily dose (no lower than the minimum specified dose) for 7 ± 2 days that, in the opinion of the Investigator, has demonstrated acceptable tolerability and seizure control. Fewer than 3 TVs may be needed before entry into the Evaluation Period, depending on the BRV dose at which acceptable tolerability and seizure control is demonstrated.

Based on tolerability and seizure control, a subject's BRV dose may be reduced to no lower than the designated minimum dose indicated in [Table 7-1](#). If a subject had previously received the

reduced BRV dose for 7 ± 2 days with acceptable tolerability and seizure control, then the subject may enter directly into the Evaluation Period.

Table 7-1: Recommended BRV dosing schedule for directly enrolled subjects during the Up-Titration Period

Visit (Week)	BRV dose per dosing occasion (mg/kg)	BRV dose per day (mg/kg/day)
TV1 (1)	~0.5	~1.0
TV2 (2)	~1.0	~2.0
TV3 (3)	~2.0	~4.0

BRV=brivaracetam; TV=Titration Visit; “~”=approximately

Daily doses will not exceed the maximums of 50mg/day, 100mg/day, and 200mg/day for Weeks 1, 2, and 3 of up-titration, respectively.

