1 SUMMARY

This is a Phase 3, open-label, single-arm, multicenter, long-term study to evaluate the safety and efficacy of brivaracetam (BRV) in children with epilepsy. This study is designed for pediatric subjects ≥ 1 month to <17 years of age who have completed other pediatric BRV studies (herein referred to as “long-term follow-up” [LTFU] subjects) and for at least 100 subjects ≥ 4 years to <17 years of age with POS who had not previously enrolled in a pediatric BRV study (herein referred to as “directly enrolled subjects”), with a planned total enrollment of approximately 600 subjects.

The primary objective is to document the long-term safety and tolerability of BRV. The secondary objective is to assess the efficacy of BRV during long-term exposure. The other objectives are to explore direct cost parameters and to assess the effect of BRV 1) on behavior and cognition using the age-appropriate Achenbach Child Behavior Checklist (CBCL/1½-5 or CBCL/6-18) for LTFU subjects ≥ 18 months of age at Baseline of their initial BRV study (herein referred to as their “core study”) and for all directly enrolled subjects, 2) on cognition using the Behavior Rating Inventory of Executive Function® (BRIEF®)/BRIEF®-Preschool Version (BRIEF®-P), and 3) on quality of life using the Pediatric Quality of Life Inventory™ (PedsQL™) for LTFU subjects ≥ 2 years of age at the Baseline of the core study and for all directly enrolled subjects. The Bayley Scales of Infant and Toddler Development®, Third Edition (Bayley-III®) will be used to assess LTFU subjects enrolled in English-speaking countries and in countries where a validated translation is available and <18 months of age at Baseline of the core study; the Bayley-III will not be used to assess directly enrolled subjects since all are to be ≥ 4 years of age.

The LTFU subjects will enter directly into the Evaluation Period at the Entry Visit (EV) and will continue BRV treatment at the individualized dose they were receiving at the completion of their core study. Directly enrolled subjects will enter N01266 at the Screening Visit (ScrV) and then participate in up to 3 weeks of an Up-Titration Period. If a directly enrolled subject demonstrates, in the opinion of the Investigator, acceptable tolerability and seizure control on the same daily dose of BRV (no lower than 1mg/kg/day) for 7 ± 2 days during the Up-Titration Period, the subject will attend the EV and enter the Evaluation Period on that dose.

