Brivaracetam (tablet and oral solution) should be administered twice daily (bid) in 2 equally divided doses. All LTFU subjects must be able to tolerate the minimum dose specified in the core study to be eligible for entry into the Evaluation Period of N01266. All directly enrolled subjects must be able to tolerate at least 1mg/kg/day during the Up-Titration Period prior to entering the Evaluation Period of N01266, as indicated in Section 7.2.

The maximum allowable BRV dose is 5.0mg/kg/day (2.5mg/kg bid), not to exceed a dose of 200mg/day. Subjects will receive oral solution or tablets, as appropriate. With the exception of dose adjustments for BRV during the Up-Titration Period, which should be made in accordance with the protocol-specified guidelines, dose adjustments of BRV and any concomitant antiepileptic drugs (AEDs) are allowed at any time based on clinical judgment.

Subjects will receive BRV treatment in this study for at least 3 years, until approval of BRV has been obtained for pediatric subjects in their age range, until a managed access program is

established as allowed per country-specific requirements in addition to legal and regulatory guidelines, until subjects transition to another BRV study, or until the investigational product development in the related age range of the pediatric population is stopped by the Sponsor, whichever comes first.

For LTFU subjects, the EV is the first study visit. For directly enrolled subjects, the EV occurs after subjects have completed the ScrV and at least 1 Titration Visit (TV), and have maintained acceptable tolerability and seizure control on the same daily dose of BRV (no lower than the minimum specified dose) for 7 ± 2 days of the Up-Titration Period. For subjects who continue in this study until it ends, the Evaluation Period will extend from the EV until the final evaluation visit (Final Visit, FV). For subjects who prematurely discontinue the study, the Evaluation Period will last from the EV until the Early Discontinuation Visit (EDV), followed by a maximum 4-week Down-Titration Period, a 2-week Safety (Drug-Free) Period, and a final Safety Visit (SV). Subjects already enrolled in N01266 may participate in EP0065 (an intravenous [iv] BRV study for pediatric subjects), if eligible, and then resume participation in N01266.

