5.4 Rationale for study design and selection of dose

N01266 will allow BRV long-term safety and tolerability data to be collected from pediatric subjects with epilepsy who will have participated in core studies and now have the opportunity to continue BRV treatment, and from directly enrolled subjects with POS. The safety and efficacy data collected in this study will support the applications for BRV indications in pediatric patients.

Each LTFU subject will begin treatment in N01266 at the individualized BRV dose he/she was receiving at the completion of the core study. Enrolled subjects who volunteer to participate in EP0065 will resume dosing in N01266 in accordance with the individualized dose they received at the completion of EP0065. Directly enrolled subjects will participate in up to 3 weeks of an Up-Titration Period. If a subject demonstrates, in the opinion of the Investigator, acceptable tolerability and seizure control on the same daily dose of BRV for 7 ± 2 days during the Up-Titration Period, the subject will be allowed to enter the Evaluation Period (subject must be able to tolerate the minimum dose of 1mg/kg/day; see Section 7.2).

A physiologically-based PK model (N01313) was developed to predict the doses to be tested in N01263. The same doses that were used for up-titration in N01263 will be used for the 3 consecutive weeks that comprise the Up-Titration Period of N01266. Based on the PK analyses performed on the plasma samples collected in N01263, the plasma concentrations approximating the concentrations for adults receiving BRV 200mg/day were not achieved by the dosing scheme initially included in N01266; as a result, it was recommended that the same doses are to be administered in all pediatric subgroups, ≥ 1 month to ≤ 16 years of age. For all subjects, the approximate doses to be administered are 0.5, 1, and 2mg/kg bid (1, 2, and 4mg/kg/day, respectively), with the daily doses not exceeding the maximums of 50mg/day, 100mg/day, and 200mg/day for Weeks 1, 2, and 3 of up-titration, respectively. The dose selection was based on the following observations:

- The PK of BRV is linear and of low variability in adults up to 1 order of magnitude above the therapeutic dose range.
- Efficacious doses in adults are expected to be from 50mg/day up to 200mg/day.

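### For directly enrolled subjects clearly above 50 kg, the Week-1 cap of 50 mg/day lies below the 1 mg/kg/day entry minimum, which has no weight exception

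*Protocol*

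**What the plan says.** The entry minimum for directly enrolled subjects is stated several times in the Protocol. Section 1 requires acceptable tolerability and seizure control "on the same daily dose of BRV (no lower than 1mg/kg/day"), held for 7 ± 2 days. Sections 1, 5.1 and 5.4 also require these subjects to "tolerate at least 1mg/kg/day during the Up-Titration Period prior to entering the Evaluation Period of N01266, as indicated in Section 7.2". Section 5.4 adds that the "subject must be able to tolerate the minimum dose of 1mg/kg/day; see Section 7.2". None of these statements has a weight exception.

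Section 7.2.1 holds the operative dosing. Table 7-1 gives steps of approximately 1.0, 2.0 and 4.0 mg/kg/day for Weeks 1, 2 and 3, and the line beneath it reads "Daily doses will not exceed the maximums of 50mg/day, 100mg/day, and 200mg/day for Weeks 1, 2, and 3 of up-titration, respectively". Section 5.4 states the same caps: "with the daily doses not exceeding the maximums of 50mg/day, 100mg/day, and 200mg/day for Weeks 1, 2, and 3 of up-titration".

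Two routes lead to entry at the lowest step. Sections 5.1, 7.2.1 and 8.3 allow entry after a single Titration Visit. Section 7.2.1 also says the "dose may be reduced to no lower than the designated minimum dose indicated in" Table 7-1, and allows direct entry if that lower dose was already held with acceptable results.

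For down-titration only, Sections 5.1 and 7.2.3 put 50 mg/day beside 1 mg/kg/day as the equivalent for body weights above 50 kg.

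**The concern.** One rule is a floor in mg/kg and the other a ceiling in mg, and they cross at 50 kg. Above that weight the lowest titration step can no longer reach the floor. Directly enrolled subjects are 4 to under 17 years old, and Sections 6.1 and 6.2 set no weight limit, so adolescents of 60 kg or more are eligible.

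What is at stake is the dose given before entry. An adolescent of 70 kg who is controlled on 50 mg/day, or who tolerates 100 mg/day poorly and would step back, has a sound clinical reason to enter on 50 mg/day. A site that applies the stated minimum literally would have to give more drug than that subject needs, or not admit the subject to the Evaluation Period. A site that reads the rule by its probable intent would admit the subject on 50 mg/day.

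**Working it through.** Inputs:

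- Entry minimum: 1 mg/kg/day (Sections 1, 5.1, 5.4).
- Step targets: about 1, 2 and 4 mg/kg/day (Table 7-1).
- Caps: 50, 100 and 200 mg/day for Weeks 1, 2 and 3 (Sections 5.4 and 7.2.1).
- Body weights of 55, 60, 70, 80 and 100 kg are illustrative assumptions. The Protocol gives no weight distribution.

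Formula: highest dose per kg at a step = min(cap, target × weight) / weight.

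The Protocol's own figures come first. At 50 kg the three steps give min(50, 50)/50 = 1.00, min(100, 100)/50 = 2.00 and min(200, 200)/50 = 4.00 mg/kg/day. These are the Table 7-1 values, so the caps and the mg/kg steps agree exactly at 50 kg.

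Above 50 kg every cap binds:

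| Weight (kg) | Week 1: 50/weight | Week 2: 100/weight | Week-1 floor met? |
|---|---|---|---|
| 55 | 0.91 | 1.82 | no, though arguably approximately 1 |
| 60 | 0.83 | 1.67 | no |
| 70 | 0.71 | 1.43 | no |
| 80 | 0.63 | 1.25 | no |
| 100 | 0.50 | 1.00 | no |

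At 60, 70 and 80 kg the Week-1 dose is 17%, 29% and 38% short of 1 mg/kg/day (1 − 50/weight).

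The lowest dose that meets a literal 1 mg/kg/day is 60, 70 and 80 mg/day at these weights, which is weight/50 − 1 = 20%, 40% and 60% above the Week-1 cap. The recommended Week-2 step is min(2 × weight, 100) = 100 mg/day at all three weights, double the Week-1 dose.

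The floor can be met in Week 2 when 100/weight ≥ 1, that is up to 100 kg, and in Week 3 when 200/weight ≥ 1, up to 200 kg.

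For the step-back route, the sentences about tolerating 1 mg/kg/day might be met by a subject who tolerated a higher step and then came down. The Section 1 sentence is stricter: it sets the floor on the dose that was held and on which the subject enters. A subject of 60 kg entering on 50 mg/day does not meet it.

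With the down-titration equivalent added, the minimum above 50 kg becomes 50 mg/day. This equals the Week-1 cap at every such weight, and the inconsistency disappears.

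**The case against.** The strongest reply is that Section 7.2 already answers the question. The minimum sentences point there, the 50 mg/day cap is printed directly under Table 7-1, and Section 5.4 joins the approximate mg/kg doses and the caps in one sentence. The natural reading is then a lowest step of about 1 mg/kg/day, up to 50 mg/day. The down-titration text supports this, and so does the 50 mg/day lower end of the adult range in Section 5.4. As evidence of intent this stands. It does not repair the text: Section 7.2.1 names a minimum only by reference to a mg/kg figure, and a maximum does not redefine a minimum. The approximation sign in Table 7-1 may cover a subject just over 50 kg, but hardly a shortfall of 17% or more, and Section 1 puts no approximation on its floor.

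It can also be said that tablet dosing makes the mg/kg figure nominal, because Section 7.2 says "The mg dosage for the oral tablet treatment should be calculated to match as closely as possible the mg/kg based dosage". That rule deals with rounding to the allowed tablet doses. Oral solution could deliver 60 mg/day at 60 kg, so the shortfall here comes from the cap. For the same reason, tablet rounding below 50 kg is a separate matter, already covered by Section 7.2, and adds nothing to this point.

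Two stronger readings are tempting, and the document supports neither.

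- A reader might infer that the two rules cannot both be met and that heavier adolescents are shut out. They can both be met at Week 2 up to 100 kg. Allowing entry after one Titration Visit does not promise that every subject can use that route.
- A reader might infer that entry on 50 mg/day above 50 kg would be classed as a protocol deviation. Section 12.6 leaves the criteria for important deviations to the project Data Cleaning Plan, which is not at hand, and the Protocol does not say how such an entry would be classed.

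**Conclusion.** The entry minimum is wrong as written for directly enrolled subjects clearly above 50 kg. Taken literally it withholds the lowest titration step, both as a first entry dose and as a dose to return to, and requires at least 20%, 40% and 60% more drug than the Week-1 cap at 60, 70 and 80 kg. The conclusion rests on the literal wording of Section 1 and on weights assumed for illustration; how many subjects reach them is unknown.

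This is a minor correction to a dosing and entry threshold. Its value is to protect heavier adolescents from escalation they do not need. The dose can be adjusted after entry (Section 7.2.2), the Safety Set is unaffected, no primary variable is redefined, and there is no formal sample size calculation to disturb.

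**What to change.** In Sections 1, 5.1, 5.4 and 7.2.1 with Table 7-1, state the entry minimum as 1 mg/kg/day, followed by a parenthesis giving 50 mg/day for subjects with body weights above 50 kg. Sections 5.1 and 7.2.3 already use this form for down-titration, so no new dosing judgment is needed. The cost is one parenthesis in four sections and a short clarification letter to sites.

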7.2.2 Evaluation Period for all subjects

The maximum BRV dose will be 5.0mg/kg/day (2.5mg/kg bid), not to exceed a dose of 200mg/day. Subjects may receive oral solution or oral tablets, as appropriate.

The LTFU subjects will ordinarily start dosing in N01266 on the individualized BRV dose they were receiving at the completion of the core study; enrolled subjects who volunteer to participate in EP0065 should resume dosing in N01266 on the individualized BRV dose they were receiving at the completion of EP0065. Subjects must be able to tolerate the minimum BRV dose specified in the core study to be eligible for entry into the Evaluation Period of N01266.

Dose can be adjusted at any time as considered necessary by the Investigator and required by the subject’s medical condition. The newly adjusted dose must not exceed the maximum allowed dose (5mg/kg/day [2.5mg/kg bid], not to exceed a dose of 200mg/day).

7.2.3 Down-Titration Period

All subjects who prematurely discontinue the study should complete an EDV and have their BRV dose down titrated by a maximum of half the dose every week for a maximum of 4 weeks until a dose of 1mg/kg/day (50mg/day for subjects with body weights $>50\text{kg}$) is reached.

Equally, all subjects completing the study but switching to treatment other than BRV should have their BRV dose down titrated.

7.2.4 Alternative study treatment supply due to COVID-19

When a subject can no longer return to the study site but will continue in the study, the following methods may be used to provide study treatment:

- Site to subject: In instances where site staff can ship study treatment dispensed from the site or pharmacy supply directly to the subject, or
- Depot to subject: In instances where it is not possible for the site staff to access study treatment and/or ship study treatment dispensed from the site or pharmacy supply directly to the subject.

7.3 Packaging

Oral solution (10mg/mL) will be packaged in 300mL type III amber glass bottles with child-resistant tamper evident polypropylene (PP) screw closures. Measuring devices, 1mL, 3mL, and 10mL syringes, will be provided as necessary with an adaptor able to fit all the bottle sizes.

Oral tablets of BRV 10mg, 25mg, and 50mg will be packaged in high-density PP bottles with child-resistant PP screw closures.

7.4 Labeling

Clinical drug supplies will be labeled in accordance with the current International Council for Harmonisation (ICH) guidelines on Good Clinical Practice (GCP) and Good Manufacturing Practice and will include any locally required statements. If necessary, labels will be translated into the local language.

The labels will be adapted to the size of the IMP bottles.

7.5 Handling and storage requirements

The Investigator (or designee) is responsible for the safe and proper storage of IMP at the site. Investigational medicinal product stored by the Investigator is to be kept in a secured area with limited access, according to the storage conditions mentioned in the label.

Appropriate storage conditions must be ensured either by the temperature (eg, room, refrigeration unit) or by completion of a temperature log in accordance with local requirements on a regular basis (eg, once a week), showing actual and minimum/maximum temperatures reached over the time interval.

In case an out-of-range temperature is noted, it must be reported as per instructions contained in the IMP Handling Manual.

The Investigator (or designee) will instruct the subject to store the IMP following the instructions on the label.

7.6 Drug accountability

A Drug Accountability form will be used to record IMP dispensing and return information on a by-subject basis and will serve as source documentation during the course of the study. Details of any IMP lost, damaged (due to breakage or wastage), not used, partially used, disposed of at the study site, or returned to the Sponsor or designee must also be recorded on the appropriate forms.

All supplies and pharmacy documentation must be made available throughout the study for UCB (or designee) to review.

Investigational medicinal product intended for the study cannot be used for any other purpose than that described in this protocol.

The Investigator (or designee) is responsible for retaining all used, unused, and partially used bottles of IMP until returned or destroyed.

The Investigator may assign some of the Investigator's duties for drug accountability at the study site to an appropriate pharmacist/designee.

The Investigator must ensure that the IMP is used only in accordance with the protocol.

Periodically, and/or after completion of the clinical phase of the study, all used (including empty containers)/partially used, unused, damaged, and/or expired IMP must be reconciled and either destroyed at the site according to local laws, regulations, and UCB SOPs or returned to UCB (or designee). Investigational medicinal product intended for the study cannot be used for any other purpose than that described in this protocol.

7.7 Procedures for monitoring subject compliance

The IMP (oral solution or oral tablets) will be supplied to the subject/parent(s)/legal representative(s) at the TV(s) (directly enrolled subjects only), EV, MEV, FEV, YEV, and at the EDV in the case of early discontinuation. The IMP for down-titration will be dispensed at the FV for subjects who complete the study but do not continue BRV treatment.

The Investigator will instruct the subject/parent(s)/legal representative(s) to bring back at each visit the bottles (even empty) dispensed at the previous visit and containing all the remaining tablets or oral solution.

Drug accountability must be done in the parent(s)/legal representative(s), and when possible, the subject's presence in order to obtain explanations regarding discrepancies in compliance with the dosing regimen. Drug accountability must be recorded on the Drug Accountability form.

If a subject is found to be persistently noncompliant in the Investigator's opinion, the Sponsor in conjunction with the Investigator will make a decision as to whether the subject should be withdrawn from the study.

Study drug compliance will be assessed at the TV(s) and EV (directly enrolled subjects only), MEV, FEV, YEV, FV, and at the EDV and the Down-Titration Visit (DTV) in the case of early discontinuation.

The number of tablets and the quantity of the oral solution dispensed and returned must be recorded in the source documents.

